### **3.2 Sample Size**

The study will enroll 8 participants.

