#### **4.4 Laboratory Samples**

Female participants of childbearing potential must produce a negative urine pregnancy test on Day 1 prior to dosing. Results from pregnancy tests performed within 3 days prior to Day 1 will be accepted for eligibility. Due to the teratogenic potential of omadacycline, a urine pregnancy test must be repeated and confirmed negative on Day 5 prior to infusion. Omadacycline dosing will be discontinued if the Day 5 pregnancy test is positive.

Participants will provide a total of 13 stool samples and 12 saliva samples during study participation. Two stool samples (one before and one after dosing) and one saliva sample will be provided on Day 1. On Days 2-10, Day 13 (+1), and Day 31 ( $\pm 1$ ) participants will provide the first stool sample of the day and one saliva sample per study day. Participants should deliver any home-collected stool samples to the clinic by 4:30pm on the day of collection and should store the sample in the refrigerator if not immediately bringing to the clinic. If the first stool sample of the day is collected after 4:30pm, it may be stored in the refrigerator overnight and delivered to the clinic the next morning.

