#### *High-throughput metagenomics sequencing:*

Microbiome characterization will be performed by sequencing the V3-4 region of the 16S rRNA gene followed by extensive bioinformatics analysis related to microbial composition, diversity, and community structure. Microbial DNA extraction, 16S rRNA gene-based next-generation sequencing (using the Illumina MiSeq), quality filtering, and microbiome-based analysis will be performed [8]. Each sample will be amplified using a

barcoded primer, which yields a unique sequence identifier tagged onto each individual sample library. Illumina-based sequencing will yield > 15,000 reads per sample. Operational taxonomic units (OTUs) will be defined as  $\geq 99\%$  identity. To analyze differences across timepoints, the OTU table will be normalized to the lowest number of sequences per sample, then consolidated by summing to species level and to each successively higher taxonomic level. The alpha diversity parameters Chao and Shannon (based on number of OTUs) and Phylogenetic Diversity (PD) (based on phylogenetic relationships), will be generated in QIIME or R; alpha diversity is widely regarded as an indication of microbiota health. For beta diversity, which describes the relationships between samples, weighted Unifrac distance matrices will be generated in QIIME.

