## 6.2 Statistical analyses

In general, the healthy volunteer analyses will assess changes in total and species-specific microbiota over time as well as changes in microbial diversity. Significance differences over time will be calculated using Mann-Whitney U test. Analyses will be performed using SAS (SAS Institute, Cary NC) or R on log-transformed data. The LEfSe (Linear Effect Size) algorithm [9] will be used to identify significant differences in microbiota composition between baseline and each study time point, followed by Wilcoxon Signed Rank tests on identified taxa. The Benjamini-Hochberg procedure will be used to control the false discovery rate at 0.10 [10]. The MaAsLin algorithm will be used to find associations of taxa with treatment. For beta diversity, principal co-ordinates analyses on weighted Unifrac distance matrices generated in QIIME will be performed in the vegan package in the statistical program R. Finally, using the methods described by Burdet et al, Shannon diversity (a measure of alpha diversity) will be compared at each time point for subjects that receive moxifloxacin or comparators[11].

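### Re-testing only the LEfSe-selected taxa in the same samples does not guarantee the stated false discovery rate of 0.10

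*Combined protocol and SAP*

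**What the plan says.** Section 6.2 describes taxon-level analysis in several ways.

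- The general aim is that "the healthy volunteer analyses will assess changes in total and species-specific microbiota over time", and the first test named is unpaired: "Significance differences over time will be calculated using Mann-Whitney U test".
- LEfSe is then used to "identify significant differences in microbiota composition between baseline and each study time point, followed by Wilcoxon Signed Rank tests on identified taxa".
- The sentence after that states the error rate: "The Benjamini-Hochberg procedure will be used to control the false discovery rate at 0.10".
- A further tool follows: "The MaAsLin algorithm will be used to find associations of taxa with treatment".

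The section does not say which tests form the BH family: all taxa or the selected ones, one time point or all of them, Mann-Whitney or signed-rank. It gives no LEfSe cut-off and describes no hold-out or split sample.

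Section 6.1 says the sequence table is "consolidated by summing to species level and to each successively higher taxonomic level", so several taxonomic levels could be tested; the number of taxa is not given. Section 3.2 fixes the size: "The study will enroll 8 participants". Section 4.4 gives the sampling: "Participants will provide a total of 13 stool samples and 12 saliva samples during study participation". One stool sample is taken before dosing, which leaves 13 − 1 = 12 contrasts with baseline.

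**The concern.** BH holds its rate when the p-values of unchanged taxa are valid, that is, not already pushed towards zero. Here the signed-rank test is applied only to taxa that have just shown a difference in the same samples for the same contrast. An unchanged taxon reaches the second test because its data happened to look different, so its signed-rank p-value is likely to be small as well. BH over the survivors does not count the taxa examined and discarded in the screen.

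At a time point where no taxon truly changes, every listed taxon is noise, yet the report would carry a 10% false discovery rate. The damage is limited to the taxon lists. The primary objective (section 1.1.1) is descriptive, no decision rests on a named taxon, and the alpha and beta diversity results are untouched.

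**Working it through.** **Inputs from the documents.** 8 pairs per contrast (section 3.2), 12 contrasts (section 4.4), BH at 0.10 (section 6.2). The plan gives no calculation behind the 0.10 that could be reproduced.

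**Assumptions.** 50, 100 or 200 independent taxa; values normal on the log scale; within-subject correlation ρ of 0.3, 0.5 or 0.7; an unpaired Kruskal-Wallis test at 0.05, with no effect-size cut, standing in for LEfSe. Shifts are in SD of the log-scale values.

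**Formulas.** The false discovery rate (FDR) is E[V / max(R, 1)], with V false and R total listed taxa. If nothing changes, V = R and the FDR equals the chance of listing at least one taxon. BH over s tests lists the k smallest p-values for the largest k with p(k) ≤ 0.10 × k / s.

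**By hand.** The smallest two-sided signed-rank p-value with 8 pairs is 2/2⁸ = 2/256 = 0.0078.

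- BH over s selected taxa: a single taxon at that minimum is listed if 0.0078 ≤ 0.10/s, which holds up to s = 12. If only one taxon is selected, any p ≤ 0.10 suffices.
- BH over all 100 taxa: 0.10 × k/100 ≥ 0.0078 needs k ≥ 7.8, so at least 8 taxa must be listed together.

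The choice of family therefore decides the result. With 100 unchanged taxa and ρ = 0.5, on average 1.19 pass the screen and 0.99 are still listed after BH. That is 0.99/1.19 = 83%, so the second step removes little.

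**Simulated FDR, BH over selected taxa, one time point** (2,000 to 3,000 trials per setting):

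| Setting | ρ = 0.3 | ρ = 0.5 | ρ = 0.7 |
|---|---|---|---|
| 50 taxa, none changed | 0.61 | 0.38 | 0.14 |
| 100 taxa, none changed | 0.83 | 0.62 | 0.26 |
| 200 taxa, none changed | 0.96 | 0.84 | 0.46 |
| 5 of 100 shifted 1 SD | 0.44 | 0.28 | 0.10 |
| 5 of 100 shifted 2 SD | 0.26 | 0.14 | 0.05 |
| 20 of 100 shifted 1 SD | 0.16 | 0.08 | 0.03 |
| 20 of 100 shifted 2 SD | 0.07 | 0.04 | 0.01 |
| 100 taxa, none changed, 0.01 screen | 0.22 | 0.08 | 0.01 |
| 100 taxa, none changed, mean-difference cut of 1 SD | 0.61 | 0.23 | 0.01 |
| 100 taxa, none changed, mean-difference cut of 1.5 SD | 0.03 | 0.00 | 0.00 |

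With 100 unchanged taxa, the mean number of false taxa is 1.9, 1.0 and 0.3; ρ of 0.8 or 0.9 gives an FDR of 0.10 or 0.01. With taxa in correlated blocks of 5 (between-taxon correlation 0.7), the no-change figures are 0.73, 0.53, 0.23. A separately coded repeat agreed within simulation error.

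**Other readings of the BH sentence, 100 taxa.**

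- BH over all screened taxa, with p = 1 for those not selected: no false taxon in any no-change run. With 5 taxa shifted 2 SD it finds at most 0.2% of them; with 20 shifted, 85–99%.
- BH over Mann-Whitney tests of all taxa: no-change rate 0.016, 0.003, 0.000. With 5 changed it finds 64–65% of 2 SD taxa and 2–3% of 1 SD taxa, because the pairing is ignored.

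**The case against.** **The defect depends on a reading.** The BH sentence is attached to no test. That it covers only the selected taxa is inferred from its position after the signed-rank step, and two other readings keep the rate. This stands, and it is why the conclusion is conditional. But the text does not exclude the natural reading, and it states an error rate without saying what it applies to.

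**A full null is the least relevant case.** Days 2 to 10 are on drug, Day 13 is three days after the last dose, and section 2.0 expects antibiotics to disturb the microbiota. No change at all is most plausible at the Day 1 post-dose sample and perhaps Day 31. With broad change the rate holds: 30 of 100 taxa shifted 1 SD gives 0.10, 0.06, 0.02. This also stands, and it limits the size. It does not restore a guarantee for time points with little or sparse change.

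**LEfSe involves an effect size, which the base case ignores.** With 5 of 100 shifted 2 SD, a 1 SD cut brings the FDR to 0.13, 0.04, 0.00, and a 1.5 SD cut to 0.00 throughout. Because the plan states no cut-off, this shows sensitivity to the choice, not protection.

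**Replacing the inferential test goes further than the defect requires.** It costs power, and section 6.2 gives MaAsLin a differently worded role. That is a fair reason to offer the wording-only repair as well.

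**Conclusion.** The concern holds as a minor one. Read in its natural order, section 6.2 selects taxa and re-tests them in the same eight participants, and then claims an error rate which that sequence does not guarantee. That conclusion is firm.

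The size is not. Under the assumptions above, the FDR runs from far over 0.10 (0.83, 0.62, 0.26 for 100 unchanged taxa) to below it when many taxa change, when within-subject correlation is high, or when the cut-off is strict. It would be wrong to say that the rate will exceed 0.10. Where a few taxa change by 2 SD, most listed taxa are usually real: more than half were false in 2.5%, 0% and 0% of runs with 5 of 100 shifted 2 SD, against 32%, 13% and 2% at 1 SD. The figures rest on a stand-in for LEfSe and on an assumed number of taxa.

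**What to change.** **Main fix.** For each post-baseline time point, make one paired test of every taxon passing a prevalence filter, set without reference to time point, the inferential analysis. MaAsLin is already named: fit it to the Day 1 pre-dose samples and that time point's samples, with a fixed participant factor. Apply BH at 0.10 within each time point over all those taxa, and state the taxonomic level or levels. Label the LEfSe, signed-rank and taxon-level Mann-Whitney results descriptive.

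In simulation this was run as a paired t-test, which gives the same p-values as a least-squares fit with a participant factor (7 df). With 100 taxa, the no-change rate was 0.09–0.11 (0.05–0.06 with heavy-tailed or skewed errors), and the FDR was 0.09–0.10 with 5 changed.

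**Cost.** No new samples, but the time term, participant factor and filter must be written down. The downsides are:

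- Fewer taxa are found when change is sparse. With 5 of 100 changed it finds 69%, 89%, 99% at 2 SD (plan 96–99%) and 7%, 13%, 32% at 1 SD (plan 41–45%). The plan's figures come from a procedure that does not hold its rate.
- Control is per time point. If nothing changed at any of the 12 contrasts, the chance of a false taxon somewhere would be 0.67–0.70 (mean 1.3–1.6 false taxa), against 0.94–1.00 (mean 22, 12, 4) for the plan (300 trials).
- With 20 of 100 shifted 2 SD, its FDR of 0.08 is no better than the plan's.
- It relies on approximate normality on the log scale. With half the values at a floor it was conservative (no-change rate 0.002–0.006) and found 59–91% of 2 SD taxa but only 2–5% of 1 SD taxa.

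**Simpler alternative, wording only.** Keep the two steps, state the LEfSe cut-off, drop the claim that the FDR is controlled at 0.10, and call those p-values descriptive.

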## 2.0 BACKGROUND AND SCIENTIFIC RATIONALE

*Clostridioides difficile* infection is a major health threat in the United States that is most often an outcome of perturbation of gut microbiota following antibiotic use [1]. Even the limited number of antibiotic regimens effective in the treatment of *C. difficile* infection have the ability to impact gut microbiome in a negative way and may increase the risk of relapse due to such perturbations [2,3,4]. Thus, there is an increasing need to identify candidate therapies for *C. difficile* that target this pathogen but have minimal effect on the native gut microbiome.

Omadacycline is an aminomethylcycline tetracycline antibiotic that is approved by the US Food and Drug Administration (FDA) for the treatment of community-acquired bacterial pneumonia (CABP) and acute bacterial skin and skin structure infections (ABSSSI) [5]. A recent study demonstrated *in vitro* activity of omadacycline against *C. difficile* [6].

Given the clinical need to improve upon current antibiotic regimens for the treatment of *C. difficile* infection with a particular focus on the impact of therapies on gut microbiome, we propose this study to characterize the impact of IV omadacycline on gut microbiome of healthy volunteers. We plan to enroll healthy volunteers between the ages of 18 and 40 years old and without history of cardiovascular, gastrointestinal, hepatic, or renal disease to receive 5 days of intravenous omadacycline followed by 5 days of oral omadacycline.

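### Section 6.2 does not define the Benjamini-Hochberg family. With 8 pairs, signed-rank testing over all taxa misses sparse changes, and over LEfSe-picked taxa the 0.10 false discovery rate is not assured

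*Combined protocol and SAP*

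**What the plan says.** Section 3.2 fixes the size: "The study will enroll 8 participants". No power or precision argument is given.

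Section 4.4 sets the sampling: "Participants will provide a total of 13 stool samples and 12 saliva samples during study participation". One stool precedes the first dose and 12 follow it.

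Under the sequencing heading of section 6.1, the OTU table is "consolidated by summing to species level and to each successively higher taxonomic level". The number of taxa is not stated.

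Section 6.2 uses LEfSe to "identify significant differences in microbiota composition between baseline and each study time point", "followed by Wilcoxon Signed Rank tests on identified taxa". The multiplicity rule follows: "The Benjamini-Hochberg procedure will be used to control the false discovery rate at 0.10". The section does not say:

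- whether the family is every taxon examined or only those LEfSe picked;
- whether time points and taxonomic ranks are pooled or handled separately;
- whether tests are one- or two-sided.

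The same section also names MaAsLin, without model terms, and a Mann-Whitney test ("Significance differences over time will be calculated using Mann-Whitney U test"). It does not say which method decides if they disagree.

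**The concern.** A signed-rank test on 8 pairs can take only a few p-values, and the smallest is not very small. A false discovery rate procedure over many taxa asks for very small p-values unless many taxa move together. The two fit poorly, and the definition of the family decides which way the analysis fails.

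This bears on the purpose of the study. Section 2.0 looks for therapies that "target this pathogen but have minimal effect on the native gut microbiome". A drug of that kind would change few taxa. Under one reading of 6.2, a short or empty list of changed taxa could be forced by the test. Under the other, the list could hold more false entries than the stated 0.10 suggests. A reader of the results could not tell which applied.

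**Working it through.** The plan gives no figure to reproduce, so the check starts from its inputs.

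**Inputs from the plan.** 8 participants (3.2), so at most n = 8 pairs; 12 post-dose stools (4.4); Benjamini-Hochberg at q = 0.10 and signed-rank tests after LEfSe (6.2).

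**Step 1: the floor.** The smallest two-sided exact signed-rank p-value is 2/2^n, reached when all n differences have the same sign.

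| Pairs | Smallest p | Largest family in which one lone taxon passes (p ≤ 0.10/m) |
|---|---|---|
| 8 | 2/256 = 0.0078 | 12 |
| 7 | 2/128 = 0.0156 | 6 |
| 6 | 2/64 = 0.0313 | 3 |

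At n = 8 the limit lies between m = 12 (0.10/12 = 0.00833, passes) and m = 13 (0.10/13 = 0.00769, fails). A one-sided test would have floor 1/256 = 0.0039 and a limit of 25. A missing stool, or a taxon absent at both times, removes a pair and moves down the table.

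**Step 2: several taxa together.** Benjamini-Hochberg is a step-up rule, so k taxa at the floor all pass if 0.0078125 ≤ 0.10k/m, that is m ≤ 12.8k. Two taxa pass in a family of up to 25, three up to 38, four up to 51, eight up to 102. Conversely, at least 0.078125m tests must be declared together: 4 of 50, 8 of 100, 16 of 200. They need not all sit at the floor, but if they do not, more are needed. At the next attainable value, 4/256 = 0.0156, a family of 100 needs 0.015625 × 100/0.10 = 15.6, so 16.

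**Step 3: how large the family could be.** One taxon over 12 post-dose stools is already 12 tests. If 100 taxa are assumed and time points pooled, m = 1,200 and 0.078125 × 1,200 = 93.75, so 94 taxon-by-time tests must pass together. A taxon changed at all 12 stools supplies 12 of these, so about 94/12 ≈ 8 persistently changed taxa would do. A few changes, or brief ones, would not.

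**Step 4: both readings simulated.** Assumptions: 100 independent, normally distributed taxa, 8 participants, one post-dose time point, true paired change of 3 SD, and a Kruskal-Wallis screen at 0.05 standing in for LEfSe, whose threshold is not in the plan.

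| Family | Changed taxa found (1 to 5 changed) | False discovery rate, 3 changed |
|---|---|---|
| All 100 taxa | 0–4% | controlled by the procedure |
| Screened taxa only | 97–100% | about 50%, 20% and under 3% at within-person correlation 0, 0.5 and 0.8 |

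With no taxon changed, the screened procedure declared at least one false taxon in 91%, 62% and 11% of trials at those three correlations. Pooling 12 time points at correlation 0.8, with 3 taxa changed, raised the false discovery rate to 25%.

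**Step 5: is the signal in the data?** With 5 of 100 taxa changed and all 100 in the family, signed-rank found 3.8% of them. A paired t-test on the same data found 99.8%, with a false discovery rate of 9.7%. The loss comes from the capped p-value.

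**The case against.** The strongest reply is that 6.2 runs signed-rank tests only on taxa LEfSe has picked. A drug affecting few taxa then gives a small family, often under 13, in which even one taxon can pass. Step 4 bears this out. A reader might infer from the floor that the taxon analysis as planned is blind to a drug that changes only a few taxa. The documents do not support that, because it assumes an all-taxa family that 6.2 does not specify. What the reply does not rescue is the stated 0.10 rate. Screening and confirming on the same stools removes the assurance, and whether the rate holds in practice depends on a within-person correlation that nobody knows in advance.

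A reader might also take the limit of 12 tests to mean that nothing can be declared in a larger family. It applies only to a taxon standing alone, because the rule is step-up.

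Signed-rank is not the only taxon-level method. The Mann-Whitney floor for 8 against 8 is 2/C(16,8) = 0.000155, which allows a lone taxon in a family of up to 643, and MaAsLin's p-values do not have the 0.0078 floor. This stands. But Mann-Whitney ignores the pairing, and signed-rank is the step assigned to follow LEfSe.

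Finally, the objective is to characterize impact, and no rule in the plan turns an empty list into a claim of no change. Such a misreading is a risk to guard against and is not something the plan proposes.

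**Conclusion.** The point holds as a gap with consequences either way: the family is undefined, and neither reading of signed-rank plus Benjamini-Hochberg with 8 pairs reliably gives both detection of sparse changes and the stated 0.10 rate. Over all tested taxa, the family for which that rate is meant, 1 to 5 large changes among 100 taxa are almost always missed. Over LEfSe-picked taxa they are almost always found, but the false discovery rate can reach about 20% to 50%. It stays under 3% only in the favourable case of high within-person correlation and one time point.

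The floor and the limits in steps 1 and 2 are exact for two-sided tests with non-zero, untied differences. The simulated rates depend on the assumed 100 taxa, independence, normality, 3 SD change and stand-in screen. They show direction and rough size and do not forecast this study.

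**What to change.** In section 6.2:

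- Make the planned MaAsLin model the deciding taxon analysis: log-transformed abundance, period as fixed effect, participant as random effect, with degrees of freedom suited to 8 participants.
- Name one taxonomic rank and a small set of post-baseline time points or windows in advance. State sidedness.
- Apply Benjamini-Hochberg at 0.10 over all taxa tested, not only those LEfSe picked.
- If a paired t-test is used instead, compare one named post-baseline stool with the one baseline stool. Do not average several late stools against a single baseline: for skewed data the difference is then not symmetric under no change. In null simulations (100 taxa, mean of 4 late stools against 1 baseline) a false discovery appeared in 20% to 26% of trials, against 1.4% to 2.3% with one late stool. The same caution applies to a model window holding several stools, so single time points are the safer choice.
- Keep LEfSe and signed-rank as descriptive, and state that zero signed-rank discoveries will not be reported as evidence of no change.

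The cost is wording only, with no new participants or samples. The downside is that p-values below 0.0078 then rest on approximate normality with 8 participants, and the plan should say so.

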## **Protocol Synopsis**

**Title:** Effects of IV Omadacycline on Gut Microbiome

**Version:** 2.0

**Protocol Number:** 001

**Version Date:** 24APR2023

**Principal investigator:** [name]

**Accrual Target:** 8 participants

**Population:** Healthy participants between ages 18 and 40 years.

**Regimen:** Participants will receive a 10-day course of omadacycline with 5 days of intravenous therapy followed by 5 days of oral therapy.

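### Section 6.2 compares Shannon diversity between drug groups this trial does not have, and the only over-time test it names that reaches diversity is unpaired

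*Combined protocol and SAP*

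**What the plan says.** The Synopsis describes one regimen for everyone: "Participants will receive a 10-day course of omadacycline with 5 days of intravenous therapy followed by 5 days of oral therapy". Section 3.2 adds that "The study will enroll 8 participants". The objective in section 1.1.1 is to describe what this regimen does to the gut microbiome of healthy volunteers. Sections 4.2 and 4.5 give every participant the same drug.

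Section 6.2 first places microbial diversity among the quantities whose change will be assessed, and then makes these statements:

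- Over-time test: "Significance differences over time will be calculated using Mann-Whitney U test".
- Taxa: LEfSe compares baseline with each time point, "followed by Wilcoxon Signed Rank tests on identified taxa". MaAsLin is also for taxa.
- Beta diversity: an ordination, with no test named.
- Shannon diversity: by the methods of a cited study, "Shannon diversity (a measure of alpha diversity) will be compared at each time point for subjects that receive moxifloxacin or comparators".

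On sampling, section 4.4 says "Two stool samples (one before and one after dosing) and one saliva sample will be provided on Day 1", followed by one stool on each of Days 2-10, Day 13 and Day 31. Section 6.1 gives diversity some weight: "alpha diversity is widely regarded as an indication of microbiota health".

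**The concern.** Two sentences of section 6.2 do not fit the design.

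First, the only sentence that names a diversity index and says how it will be compared sets drug groups against each other. This trial has one drug. Moxifloxacin appears nowhere else in the protocol.

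Second, what remains for diversity is the general over-time sentence, and the test there is for two independent samples. The data are repeated samples from the same people. The plan uses a paired test for selected taxa but states none for diversity.

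The direction of the error matters. Section 2.0 motivates the study by the need for treatments that disturb the resident gut flora as little as possible. In that setting a missed change looks like good news, and a non-significant result from a conservative test on 8 people is easily misread as little effect.

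**Working it through.** **Part 1: the groups.** Participants enrolled: 8 (section 3.2). Drugs given: omadacycline only (Synopsis, sections 4.2 and 4.5). Participants stated to receive moxifloxacin or a comparator: 0 of 8. External cohorts described: none.

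**Part 2: the pairs.** Stools per participant: 2 on Day 1, 9 on Days 2-10, 1 on Day 13 and 1 on Day 31, total 2 + 9 + 2 = 13, which agrees with section 4.4. That is 1 pre-dose and 12 post-dose samples, or 8 × 12 = 96 pairs if complete.

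**Why the unpaired test is conservative.** With equal variance σ² and within-person correlation r, the difference between two time-point means has variance 2σ²(1 − r)/n. An unpaired test works as if it were 2σ²/n. At r = 0.5 the true variance is half of what the test assumes, and at r = 0.7 it is 0.3 of it.

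**Size of the loss.** The plan gives no power figure to reproduce. The shift (in SD), r, the two-sided 0.05 level, normal data and equal variances are all assumptions. The only error level in the plan is a false discovery rate of 0.10. Simulation with exact p-values, n = 8, 100,000 replicates per cell; rejection rate, Mann-Whitney v signed-rank, one time point against baseline:

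| Shift | r = 0 | r = 0.3 | r = 0.5 | r = 0.7 |
|---|---|---|---|---|
| 0 (no change) | 5.0% v 3.9% | 2.5% v 3.9% | 1.1% v 3.8% | 0.3% v 3.9% |
| 0.5 SD | 15% v 11% | 12% v 15% | 9% v 19% | 7% v 30% |
| 1 SD | 44% v 35% | 44% v 47% | 44% v 61% | 45% v 83% |
| 2 SD | 95% v 89% | 97% v 96% | 98% v 99% | 99% v 100% |

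**With the plan's false discovery rate.** Here Benjamini-Hochberg at 0.10 is applied to 12 Shannon comparisons. The family of 12 is an assumption, because section 6.2 defines none. Equal correlation among all 13 samples is also assumed; 20,000 replicates. With 6 of 12 points truly shifted, the share of those points declared is:

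| Shift | r = 0.3 | r = 0.5 | r = 0.7 |
|---|---|---|---|
| 0.5 SD | 4% v 8% | 3% v 11% | 2% v 19% |
| 1 SD | 27% v 36% | 26% v 52% | 26% v 79% |
| 2 SD | 96% v 96% | 97% v 99% | 98% v 100% |

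At r = 0 and 1 SD the order reverses: 30% v 24%. With no change anywhere, the chance of at least one false declaration is 2.5%, 1.0% and 0.2% for Mann-Whitney at r = 0.3, 0.5 and 0.7. For signed-rank it is 8-9%, within the 10% target.

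**Can a paired test succeed with 8 people?** The smallest two-sided signed-rank p is 2/2ⁿ, and Benjamini-Hochberg step k is 0.10k/12.

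- 8 pairs: 2/256 = 0.0078, below step 1 (0.0083). One test at the floor is enough.
- 7 pairs: 2/128 = 0.0156, below step 2 (0.0167). If every time point has 7 pairs, at least 2 of the 12 must reach the floor.
- 6 pairs: 2/64 = 0.0313, below step 4 (0.0333). At least 4 must reach it.

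**The case against.** The strongest reply concerns the second part. The over-time sentence does not itself name diversity; its scope comes from the sentence before it. Shannon diversity is also sent to a cited method, and the title in section 10.0 speaks of temporal changes in diversity, so a sound within-person analysis may be intended. This cannot be settled from the protocol, which does not write the method out. It does not rescue the sentence, because the method is applied to groups that do not exist here. An outside moxifloxacin dataset may have been meant, but none is named.

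It is also fair to say that the loss depends on inputs nobody has documented. It is small at r = 0.3 and 1 SD, close to nil at 2 SD with positive correlation, and reversed at r = 0. At the strictest Benjamini-Hochberg step, with 2 SD and r = 0.3, Mann-Whitney passes more often (78% v 69%). The objective is descriptive, and the plan has no rule for concluding no effect, so misreading a null result is a risk and not a planned inference.

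Finally, a paired plan brings its own choices. Mann-Whitney results do not change under a log transform, but signed-rank results can. If Shannon, Chao and PD each form a separate family, the chance of any false declaration when nothing changes is about 23-24% for uncorrelated indices, 19% at index correlation 0.8 and 15% at 0.95. The false discovery rate still holds within each family. These points stand and should be weighed in drafting; they do not remove the defect.

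**Conclusion.** The concern holds: section 6.2 is wrong as written and should be fixed. That the Shannon comparison has no groups follows directly from the text and rests on no assumption. That the stated over-time test ignores pairing follows from reading the opening of section 6.2 as setting the scope of the Mann-Whitney sentence, which is the natural reading.

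The error does not inflate false positives when within-person correlation is positive. Its cost is missed change, material for shifts of about 0.5 to 1 SD with correlation of about 0.5 or more, and minor outside that range. With a descriptive objective and no powered hypothesis, this is a correction to make before analysis and not a threat to the trial as a whole.

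**What to change.** Replace the last sentence of section 6.2 with text to this effect:

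> For each of the 12 post-dose stools, Shannon diversity is compared with that participant's own Day 1 pre-dose value by the exact Wilcoxon signed-rank test. Chao and PD are handled likewise. The 12 Shannon tests form one Benjamini-Hochberg family at 0.10; Chao and PD are separate families. Each time point is reported with its number of pairs and the median paired change with 95% CI.

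State the scale in advance. Section 6.2 specifies analysis "or R on log-transformed data"; if that is kept for Shannon, say how a value of zero is handled. If the chance of any false declaration across the three indices is a worry, make Shannon the lead index or pool the families.

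In the Mann-Whitney sentence, state that comparisons over time within participants use a paired test. A mixed model with a participant effect is an acceptable alternative. If the cited study's method is to be kept, write it out. If an external moxifloxacin dataset is intended, name it and label the comparison non-randomised and exploratory.

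The cost is redrafting two sentences and specifying families, scale and intervals. No samples, visits or assays are added, and both procedures are already in the plan. The drawbacks are some loss of power if within-person correlation is near zero (1 SD: 35% v 44%) and the p-value floor when pairs are missing.
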